9.6.1 Primary Efficacy Analysis

The primary efficacy endpoint will be analyzed by calculating the ORR. The ORR is defined as the proportion of patients with a documented and confirmed best overall response of CR or PR per RECIST v1.1 (or modified RECIST v1.1 for mCRPC patients) as assessed by the investigator. A confirmed CR or PR is a response that is maintained and documented on a subsequent tumor assessment at least 4 weeks after initial response.

The frequency and percentages of patients with a best overall response of CR, PR, SD, or progressive disease (PD) will be summarized. The ORR (confirmed CR+PR) will also be

summarized with frequencies and percentages. All summaries of response rates will be accompanied by 95% confidence intervals (CIs).

9.6.2 Secondary Efficacy Analysis

9.6.2.1 Duration of Response

For any patient who reaches a best confirmed overall response of CR or PR, DOR will be measured from the date that best response is first recorded until the first date that progressive disease is documented per RECIST v1.1 (or modified RECIST v1.1 for mCRPC patients). Patients without a documented event of radiologic progression will be censored on the date of the last adequate tumor assessment.

The Kaplan-Meier methodology will be used to summarize DOR. If able to be estimated, the 50th percentile (median) together with a 95% CI will be presented. The number of patients with events and the number of patients at risk at each timepoint will be presented and censored patients will be graphically displayed.

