2 STUDY OBJECTIVES AND ENDPOINTS

Primary, secondary, and exploratory objectives and endpoints are shown in [Table 1](#).

Table 1. Study Objectives and Endpoints

Objectives	Endpoints	Justifications
Primary Objective	Primary Endpoint	Justification for Primary Endpoint

To determine the ORR by tumor type, as assessed by the investigator, to be evaluated by RECIST v1.1 (or by RECIST v1.1 and Prostate Cancer Working Group Guidelines Version 3 [PCWG3] in patients with mCRPC).
	
Best overall response as assessed by the investigator by RECIST v1.1 (or by RECIST v1.1 and PCWG3 in patients with mCRPC).
	
Best overall response is summarized across patients as ORR, which is the proportion of complete responses and partial responses confirmed in patients with measurable disease and is a direct measure of the drug’s anti-tumor activity. It is commonly used in Phase 2 trials. It excludes stable disease, which may be more reflective of the natural history of the disease rather than response to the investigational drug.

Secondary Objectives	Secondary Endpoints	Justifications for Secondary Endpoints

1. To assess ORR by independent radiology review (IRR).
	
1. ORR as assessed by IRR (irrORR) by RECIST v1.1 (or by RECIST v1.1 and PCWG3 in patients with mCRPC).
	
1. Best overall response as assessed by IRR is summarized across patients as irrORR, which provides a measure of ORR that is devoid of the heterogeneity arising from radiology data being evaluated at various investigational sites and serves as a more independent evaluation of ORR.

2. To assess the duration of response (DOR).
	
2. DOR
	
2. DOR, defined as the time from initial tumor response to documented tumor progression, provides additional information on the longevity of tumor response.

Table 1. Study Objectives and Endpoints

Objectives	Endpoints	Justifications
3. To evaluate DCR.	3. DCR	3. DCR, defined as the percentage of complete response (CR), PR, and stable disease (SD) beyond 16 weeks, is another measure of clinical benefit to the investigational drug, being a composite of SD and ORR.
4. To estimate progression-free survival (PFS).	4. PFS	4. Defined as the duration from entry into study to objective tumor progression or death of a patient, PFS is a measure of clinical benefit.
5. To estimate OS.	5. OS	5. Defined as the duration from entry into study to death, OS is the gold standard for oncology clinical trials.

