9.6.2.3 Progression-free Survival

Progression-free survival will be calculated as the number of days from the first dose of rucaparib to documented radiologic progression, according to RECIST v1.1 (or modified RECIST v1.1 for mCRPC patients), as determined by the investigator, or death due to any cause, whichever occurs first. Patients without a documented event of radiologic progression will be censored on the date of their last adequate tumor assessment (ie, radiologic assessment), or date of first dose of rucaparib if no post-baseline tumor assessments have been performed. Only tumor scans prior to start of any subsequent anticancer treatment are included.

The Kaplan-Meier methodology will be used to summarize PFS. If able to be estimated, the 50th percentile (median) together with a 95% CI will be presented. The number of patients with events and the number of patients at risk at each timepoint will be presented, and censored patients will be graphically displayed.

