Progressive Disease:	At least a 20% increase in the sum of the LD of target lesions, taking as reference the smallest sum on study (this includes the baseline sum if that is the smallest on study). In addition to the relative increase of 20%, the sum must also demonstrate an absolute increase of at least 5 mm. The appearance of 1 or more new lesions is also considered progression.

Evaluation of Nontarget Lesions

Complete Response:	Disappearance of all nontarget lesions and normalization of tumor marker level.
Stable Disease/Incomplete Response:	Persistence of 1 or more nontarget lesion(s) or/and maintenance of tumor marker level above the normal limits.
Progressive Disease:	Appearance of 1 or more new lesions and/or unequivocal progression of existing nontarget lesions.

If tumor markers are initially above the institutional ULN, they must normalize for a patient to be considered a complete responder.

Evaluation of Best Overall Response

The best overall response is the best response recorded from the start of the treatment until disease progression/recurrence (taking as reference for PD the smallest measurements recorded since the treatment started). The patient's best response assignment will depend on the achievement of both measurement and confirmation criteria.

Evaluation of Best Overall Response			
Target Lesions	Nontarget Lesions	New Lesions	Overall Response
CR	CR	No	CR
CR	Non-CR/non-PD	No	PR
CR	Not evaluated	No	PR
PR	Non-PD or not evaluated	No	PR
SD	Non-PD or not evaluated	No	SD
Not Evaluated	Non-PD	No	NE
PD	Any	Yes or No	PD
Any	PD	Yes or No	PD
Any	Any	Yes	PD

Abbreviations: CR = complete response; NE = not evaluable; PD = progressive disease; PR = partial response; SD = stable disease.

Patients with global deterioration of health status requiring discontinuation of treatment without objective evidence of disease progression at that time should be classified as having symptomatic deterioration. Every effort should be made to document the objective progression, even after discontinuation of treatment.

In some circumstances, it may be difficult to distinguish residual disease from normal tissue. When evaluation of CR depends on this determination, it is recommended that the residual lesion be investigated (fine needle aspiration/biopsy) prior to confirming the complete response status.

Confirmatory Measurement/Duration of Response

Confirmation

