If an initial CR or PR is noted, confirmatory scans should be performed at least 4 weeks after response was first documented.

Duration of Overall Response

The duration of overall response is measured from the time measurement criteria are met for CR or PR (whichever is first recorded) until the first date that recurrent or PD is objectively documented (taking as reference for PD the smallest measurements recorded since the treatment started).

The duration of overall CR is measured from the time measurement criteria are first met for CR until the first date that recurrent disease is objectively documented.

Duration of Stable Disease

SD is measured from the start of the treatment until the criteria for progression are met, taking as reference the smallest measurements recorded since the treatment started.

Appendix 3 Modified Response Evaluation Criteria in Solid Tumors v1.1 and Prostate Cancer Working Group 3 Criteria

The RECIST v1.1 guidelines are described in Eisenhauer, et al 2009⁴⁵ and at <http://www.eortc.be/Recist/Default.htm> and PCWG3 criteria as described by Scher, et al 2016.⁴⁶

A short summary is given below.

Measurable Disease:

Tumor lesions: measurable lesions are defined as those that can be accurately measured in at least one dimension (longest diameter to be recorded) with the following:

- A minimum size of 10 mm by CT scan (CT scan slice thickness no greater than 5 mm)
- A minimum size of 10 mm caliper measurement by clinical exam (lesions that cannot be accurately measured with calipers should be recorded as nonmeasurable)
- A minimum size of 20 mm by chest X-ray

All tumor measurements must be recorded in millimeters (or decimal fractions of centimeters).

Malignant lymph nodes: To be considered pathologically enlarged and measurable, a lymph node must be ≥ 15 mm in short axis when assessed by CT scan (CT scan slice thickness recommended to be not greater than 5 mm). At baseline and in follow-up, only the short axis will be measured and followed.

Nonmeasurable Disease:

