CT scans are required for this study at screening and every 8 calendar weeks (within 7 days before or after is permitted) thereafter. Patients who have been on study at least 24 weeks, may decrease the frequency of disease/ tumor assessments to every 12 calendar weeks (within 7 days before or after is permitted).

Duration of Overall Response

The duration of overall response is measured from the time measurement criteria are met for CR or PR (whichever is first recorded) until the first date that recurrent or PD is objectively documented (taking as reference for PD the smallest measurements recorded since the treatment started), including progression in bone per PCWG3 criteria.

The duration of overall CR is measured from the time measurement criteria are first met for CR until the first date that recurrent disease is objectively documented.

Duration of Stable Disease

SD is measured from the start of the treatment until the criteria for progression are met, taking as reference the smallest measurements recorded since the treatment started.

PCWG3 Criteria for Assessment of Bone Disease

PCWG3 criteria will be used to document evidence of disease progression in bone lesions as described by Scher, et al 2016.⁴⁶

Imaging of Baseline Bone Disease

The use of bone scan as the standard for bone imaging is retained in PCWG3, with the presence or absence of metastasis recorded first. A quantitative measure of disease burden, such as lesion number, the bone scan index, or lesion area, is also suggested, recognizing that these measures require further analytical and prospective clinical validation. Changes in lesions considered metastatic on bone scintigraphy should be followed and assessed serially using a bone scan assessment form. Areas/lesions on bone scintigraphy that are suggestive can be assessed further with CT or MRI and followed separately, but such supplemental imaging should not be used to establish indicator lesions for the purposes of a trial.

Different modalities for imaging bone metastases can provide different information for the same patient. However, because of the lack of standards for reporting disease presence or changes after treatment, positron emission tomography imaging with sodium fluoride, fluorodeoxyglucose, choline, or prostate-specific membrane antigen, bone marrow MRI (body MRI), and other modalities that are in use to image bone, should be approached as new biomarkers subject to independent validation.

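### Duration of response ends only at documented progression, so a responder who dies without a progression scan is censored; relative to progression-or-death, the DOR curve is too long whenever such deaths occur

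*Combined protocol and SAP*

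**What the plan says.** Section 9.6.2.1 runs DOR "until the first date that progressive disease is documented per RECIST v1.1", or the modified criteria for prostate cancer. It then gives one censoring rule: "Patients without a documented event of radiologic progression will be censored on the date of the last adequate tumor assessment". The summary method is stated plainly: "The Kaplan-Meier methodology will be used to summarize DOR", with a median and 95% confidence interval, events, numbers at risk and a display of censored patients.

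The other definitions agree on where DOR ends:

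- Table 1 (Section 2): "DOR, defined as the time from initial tumor response to documented tumor progression".
- Appendix 2, duration of overall response: "until the first date that recurrent or PD is objectively documented".
- Appendix 3, for prostate cancer: the same end point, "including progression in bone per PCWG3 criteria".

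None of the four names death. No competing-risk analysis of DOR is planned, and no sensitivity analysis that counts deaths as events.

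For PFS, Section 9.6.2.3 takes radiologic progression "or death due to any cause, whichever occurs first" as the event. It counts only scans taken before any subsequent anticancer treatment. Section 3.1.4 follows all patients for survival every 12 weeks. Section 9.6 leaves further detail to the SAP, but the combined document has no separate SAP text on DOR.

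**The concern.** A responder who dies between scans, or deteriorates and dies before the next one, has no documented progression. Under Section 9.6.2.1 that patient leaves the risk set at the last scan, as if the response might have continued. Appendix 2 recognises the route: "Patients with global deterioration of health status requiring discontinuation of treatment without objective evidence of disease progression". The death that ends PFS for that patient does not end DOR.

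The study has a single arm and ORR as its primary endpoint, and Section 1.2.2 hopes to support a tumor-agnostic indication. DOR tells the reader how long the responses last. Responders per tumor type will be few. At the cap of 50 patients per type (Section 3.1) and an assumed ORR of 20%, the floor in Section 9.10, there would be 50 × 0.20 = 10. If all ten eventually had an event, a single death without progression would already make d = 10%.

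**Working it through.** The plan states no DOR median, event count or precision target, so there is no figure to reproduce. The check has three steps.

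**1. Follow one patient through the rules.** Take a confirmed responder who dies before progression is documented, with no subsequent therapy.

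| Endpoint | Event named | This patient |
|---|---|---|
| DOR (9.6.2.1, Table 1, Appendices 2 and 3) | Progression or recurrence only | Censored at last adequate scan |
| PFS (9.6.2.3, event definition) | Progression or death | Event at death |
| OS (9.6.2.4) | Death | Event at death |

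**2. Size of the gap between the two definitions (illustration).** Assume independent constant hazards hPD for progression and hD for death without progression, and let d = hD/(hPD + hD).

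- Median to progression or death: ln2/(hPD + hD).
- Median with deaths censored: ln2/hPD.
- Ratio: (hPD + hD)/hPD = 1/(1-d).

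The documents give neither d nor a DOR median. The table shows a range of d for assumed progression-or-death medians of 6, 9.1 and 12 months. The 9.1 is a PFS median quoted in Section 1.1.6 for another rucaparib study, borrowed only as a time scale.

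| d (assumed) | 1/(1-d) | 6 months becomes | 9.1 becomes | 12 becomes |
|---|---|---|---|---|
| 0% | 1.00 | 6.0 | 9.1 | 12.0 |
| 5% | 1/0.95 = 1.05 | 6.3 | 9.6 | 12.6 |
| 10% | 1/0.90 = 1.11 | 6.7 | 10.1 | 13.3 |
| 20% | 1/0.80 = 1.25 | 7.5 | 11.4 | 15.0 |

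**3. Check with scheduled scans.** A Kaplan-Meier simulation used 40 responders (400 repetitions), scans every 8 weeks, a total hazard of ln2/9.1 per month and assumed follow-up uniform over 6 to 30 months. The height of the curve at 12 months, progression-only against progression-or-death, was:

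- d = 5%: 45% against 43%.
- d = 10%: 47% against 43%.
- d = 20%: 51% against 42%.

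At d = 0 the two curves coincide. The simulation confirms the direction. It does not reproduce the closed-form ratios exactly, because progression can be seen only at scans about 1.8 months apart (56 days/30.44) and the simulated medians tend to fall on those dates.

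**The case against.** The strongest reply is that the four definitions agree on the end point. A duration that ends at progression is a recognisable quantity, and choosing it is not an internal error. That stands: the DOR is too long only relative to progression-or-death. But reading the Kaplan-Meier curve as time to progression requires deaths to be independent of impending progression, which is doubtful in advanced cancer, and the plan offers no analysis that shows how much depends on it.

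A reader might infer that the 1/(1-d) factor measures a bias from informative censoring. It does not. The formula assumes independence, so it gives the gap between two definitions and no more.

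A reader might also infer that deaths without progression will be common. The documents do not support that. Only confirmed responders enter DOR; Section 4.2 requires ECOG 0 to 1 and a life expectancy of at least 4 months; scans run every 8 weeks and continue when treatment stops for reasons other than progression. Directly after the sentence on global deterioration, Appendix 2 asks sites to try to document progression even after treatment has ended.

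Three further limits stand:

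- The contrast with PFS is not clean. Section 9.6.2.3 names death as an event, then repeats the censoring rule in nearly the same words. Read literally, that would censor deaths in PFS too.
- Section 9.6.2.1 starts DOR when the best response is first seen, whereas Table 1 uses the initial response and Appendix 2 the first CR or PR. For a PR that becomes a CR, the Section 9.6.2.1 start shortens DOR and partly offsets the effect described here.
- DOR is secondary and descriptive. It has no test or threshold, and the futility rule uses responses only. No landmark DOR rates are planned, so the 12-month figures above only describe the curve.

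**Conclusion.** The point holds as a matter of definition. As written, responders who die without documented progression are censored for DOR. Relative to progression-or-death, the median and curve are too long whenever such deaths occur. Under independent constant hazards the median is longer by 5%, 11% or 25% for assumed d of 5%, 10% or 20%, and by nothing at d = 0. The direction rests on the text; the size rests wholly on d, which the documents do not give.

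The documents do not support a claim that DOR will be overstated by any particular amount, nor that the plan contradicts itself on the DOR end point. This should be corrected, because the endpoint gives context to the primary result and the correction is cheap. It does not affect the ORR analysis.

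**What to change.** 1. In Table 1, Section 9.6.2.1 and Appendices 2 and 3, define the DOR event as documented progression or death from any cause, whichever comes first.
2. Censor patients alive without progression at the last adequate assessment. Censor responders who start subsequent anticancer therapy before progression at the last adequate assessment before that therapy. This follows the scan rule already in Section 9.6.2.3. Without it, a death long after a new therapy would count as a DOR event and could itself lengthen DOR.
3. Amend the matching censoring sentence in Section 9.6.2.3 so that it does not censor deaths.
4. State that DOR starts at the first CR or PR that is later confirmed, which reconciles Section 9.6.2.1 with Table 1 and Appendix 2.
5. Report how many DOR events are deaths, and keep the progression-only version as a labelled sensitivity analysis.

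The cost is a text change in five places and one extra table or curve. No new data are needed, since survival is already followed. Reported DOR may be shorter where responders die without documented progression. Item 4 works the other way and lengthens DOR for a PR that becomes a CR, so the net effect of the changes can go in either direction and should be stated openly.

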9.6.2.2 Disease Control Rate

Disease control rate (DCR) is defined as the proportion of patients that reach a confirmed CR, confirmed PR, or SD for at least 16 weeks per RECIST v1.1 (or modified RECIST v1.1 and no progression in bone by PCWG3 criteria for mCRPC patients). DCR will be summarized and accompanied by 95% CIs.

9.6.2.3 Progression-free Survival

Progression-free survival will be calculated as the number of days from the first dose of rucaparib to documented radiologic progression, according to RECIST v1.1 (or modified RECIST v1.1 for mCRPC patients), as determined by the investigator, or death due to any cause, whichever occurs first. Patients without a documented event of radiologic progression will be censored on the date of their last adequate tumor assessment (ie, radiologic assessment), or date of first dose of rucaparib if no post-baseline tumor assessments have been performed. Only tumor scans prior to start of any subsequent anticancer treatment are included.

The Kaplan-Meier methodology will be used to summarize PFS. If able to be estimated, the 50th percentile (median) together with a 95% CI will be presented. The number of patients with events and the number of patients at risk at each timepoint will be presented, and censored patients will be graphically displayed.

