3.1.4 Post-treatment Period

Upon treatment discontinuation, regardless of reason (with the exception of withdrawal of consent or death), patients will have an End-of-Treatment (EOT) Visit with assessments as detailed in [Section 7](#).

All patients will be followed for at least 28 days after the last dose of study drug and will then proceed to long-term follow-up (LTFU).

Patients who discontinue treatment for a reason other than disease progression or death should continue to have tumor scans performed at the interval specified until radiological disease progression as assessed by the investigator, death, loss to follow-up, withdrawal from study, study termination, or initiation of subsequent anticancer treatments.

Ongoing serious adverse events (SAEs), AESIs and treatment-related CTCAE Grade 3/4 AEs will be followed until resolution or stabilization has been determined, death, or loss to follow-up. After the 28-Day Follow-Up Visit, only SAEs considered as potentially related to study drug should be reported per Clovis PV requirements and captured in the Clovis Pharmacovigilance (PV) database. This includes serious reports of pneumonitis or similar events, if considered to be related to study drug.

After the 28-day Safety Follow-up Visit, AESIs of MDS and AML, irrespective of causality, should be reported per Clovis PV requirements and captured in the Clovis PV database. AESIs of pneumonitis or similar events should only be reported up to, but not beyond, the 28-day Safety Follow-up Visit.

All patients will be followed for survival and subsequent treatments every 12 weeks (\pm 14 days) relative to the last dose of rucaparib until death, loss to follow-up, withdrawal of consent or study closure.

An optional tumor biopsy will be collected from patients who experience disease progression and provide additional consent.

If a patient begins subsequent anticancer therapy, the sponsor will terminate collection of SAEs, with the exception of the AESIs of MDS and AML.

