- ^m **First dose of study drug in Cycle 1 should be administered within 3 days of enrollment.** Study treatment continues in 28-day cycles until disease progression, unacceptable toxicity, patient or physician request to discontinue, death, initiation of any other cancer therapy, positive pregnancy test, or termination of the study. Study visit should take into account the patient's rucaparib supply. A quantity of rucaparib sufficient to complete 1 cycle (28 days) should be dispensed to the subject/patient on Day 1 of each cycle.
- ⁿ AEs, SAEs, and AESIs that occur after first administration of study drug through to 28 days after last dose of study drug(s). In addition, SAEs that were related to a screening procedure will also be recorded. Ongoing SAEs, AESIs, or treatment-related Grade 3/4 AEs will be followed to resolution or stabilization. After the Safety Follow-up Visit, only SAEs considered as potentially related to study drug (including serious reports of pneumonitis or similar events, ie, interstitial lung disease, pulmonary fibrosis, acute interstitial pneumonitis, alveolitis, hypersensitivity pneumonitis, and organizing pneumonia, if considered to be related to study drug), and the AESIs of MDS and AML regardless of causality, will be recorded in the eCRF. If a patient discontinues from treatment in the rollover study and begins a subsequent anticancer therapy, the sponsor will terminate collection of SAEs.
- ^o Cycles 2 through 6 only. PK samples should be collected prior to the morning dose on the visit days, and as close as possible to 12 hours after the last dose (even if the morning dose on the specified visit days is not administered). If a new treatment cycle is delayed, the predose PK sample closest to 12 hours after the last dose should still be collected on that visit and should not be collected on Day 1 of the delayed treatment cycle. Refer to the Laboratory Manual for detailed sample collection and handling instructions.

- p An optional tumor biopsy may be collected from patients within 30 days after the time of disease progression or treatment discontinuation. Additional consent is required. Refer to the Laboratory Manual for detailed sample collection and handling instructions.

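### The PFS censoring sentence makes no exception for deaths, although death is a PFS event, and the DOR start date in section 9.6.2.1 conflicts with Appendices 2 and 3

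*Combined protocol and SAP*

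**What the plan says.** **PFS.** Section 9.6.2.3 counts days from first dose to radiologic progression "or death due to any cause, whichever occurs first". Table 1 in section 2 also treats death as an event: "Defined as the duration from entry into study to objective tumor progression or death of a patient". The sentence that follows the definition in section 9.6.2.3 sets the censoring rule: "Patients without a documented event of radiologic progression will be censored on the date of their last adequate tumor assessment". A patient with no post-baseline scan is censored at first dose. Neither branch mentions death.

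**DOR.** Section 9.6.2.1 says: "DOR will be measured from the date that best response is first recorded until the first date that progressive disease is documented". Appendix 2 and Appendix 3 start the duration of overall response when the criteria for CR or PR are met, taking whichever comes first. They define a separate duration of overall CR that starts when CR criteria are first met. Table 1 counts DOR from the initial response.

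**Progression in mCRPC (minor).** Section 7.3.3.1 says that only RECIST v1.1 determines progression. Section 3.1.3, section 9.6.2.2 and Appendix 3 also use PCWG3 criteria, which Appendix 3 applies to bone.

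**The concern.** Under section 9.6.2.3, a patient who dies without documented progression is an event by the definition and a censored observation by the next sentence. The two cannot both be programmed. If the censoring sentence is followed, the death leaves the event count and the patient is censored at the last scan, or on day 0 if there was none. A patient who dies before the first scan then contributes no follow-up at all. The resulting bias in PFS is always upward.

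For DOR, two sections give different start dates for a patient whose PR later deepens to CR. Two programmers working from different pages would report different durations from the same data.

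The study has one arm and is meant to support a tumor-agnostic indication (section 1.2.2). The PFS and DOR medians will therefore be read on their own, with no control arm in which the same definitional bias would also appear.

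**Working it through.** The plan states no PFS or DOR target, event count or power, so there is no figure of its own to reproduce. The check compares the rules and illustrates their effect.

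**1. PFS under the two readings**

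| Patient | Definition sentence | Censoring sentence, literal |
|---|---|---|
| Progression seen on a scan | Event | Event |
| Death, no progression, at least one post-baseline scan | Event at death | Censored at last adequate scan |
| Death, no post-baseline scan | Event at death | Censored at first dose |
| Alive, no progression | Not an event | Censored at last adequate scan, or at first dose if there is none |

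The readings differ only in the second and third rows.

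*Size with constant hazards.* Let λ be the total hazard of a first PFS event and f the share of first events that are deaths without progression. The documents do not give f, so it is assumed.

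- Deaths counted: median = ln 2 / λ.
- Deaths censored: Kaplan-Meier estimates a process with hazard (1 − f)λ, so median = ln 2 / [(1 − f)λ].
- Ratio = 1 / (1 − f).

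| f | Inflation of the median |
|---|---|
| 5% | 1 / 0.95 = 1.05 |
| 10% | 1 / 0.90 = 1.11 |
| 20% | 1 / 0.80 = 1.25 |

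*Effect of the scan schedule.* Scans are every 8 weeks (section 7.3.3.1), so a reported median tends to move in steps. Take an exponential first failure with true median m months, and a scan interval of D = 56 / 30.4375 = 1.84 months. The chance of failing in one interval is q = 1 − exp(−ln 2 × D / m). After scan k:

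- Deaths counted: S(k) = (1 − q)^k.
- Deaths censored at the previous scan: S(k) = (1 − h)^k, with h = (1 − f)q / (1 − fq).

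With m = 6 (assumed), q = 0.1915. Deaths counted gives S(3) = 0.5285 and S(4) = 0.4273, so the median falls at scan 4 (32 weeks). The literal reading gives S(4) = 0.4441, 0.4617 and 0.4996 at f = 5%, 10% and 20%, so the median is still scan 4.

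With m = 9.1, q = 0.1308. This is the median that section 1.1.6 reports for maintenance treatment in pancreatic cancer, and it is used here only as a second value. Deaths counted gives S(4) = 0.5709 and S(5) = 0.4962, so the median is scan 5 (40 weeks). The literal reading gives S(5) = 0.5128, 0.5300 and 0.5665, and S(6) = 0.4487, 0.4668 and 0.5057. The median moves to scan 6 (48 weeks) at f = 5% and 10%, and to scan 7 (56 weeks) at f = 20%.

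On an exact grid the median may therefore stay put or jump by one or two scans. The factor 1 / (1 − f) is a guide to the size of the bias, not a prediction.

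**2. DOR start**

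Example: PR at week 8, progression at week 40.

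| CR first seen | Section 9.6.2.1 | Appendices 2 and 3 | Difference |
|---|---|---|---|
| Week 16 (next scheduled scan) | 40 − 16 = 24 weeks | 40 − 8 = 32 weeks | 8 weeks |
| Week 24 (one scan later still) | 40 − 24 = 16 weeks | 40 − 8 = 32 weeks | 16 weeks |
| Never (best response PR) | 32 weeks | 32 weeks | 0 |

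For a PR-to-CR patient, section 9.6.2.1 yields what the appendices call the duration of overall CR, which is a different quantity from the duration of overall response. The share of such patients is not given, so the effect on the median DOR cannot be computed.

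**The case against.** **The PFS intent is clear from the same paragraph.** The definition sentence and Table 1 both count death. Almost the same censoring sentence appears in section 9.6.2.1, where it fits because DOR as defined there ends only at progression. This stands: the fault is a wording gap, and the harm arises only if a programmer follows the censoring sentence over the definition. A reader might infer that the sponsor plans to leave deaths out of PFS. The documents do not support that.

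**The SAP may settle both points.** Sections 9.1 and 9.6 leave detail to a separate SAP, which was not available. It may well do so, but the protocol text would still contradict itself, and the SAP would have to override one of its sentences.

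**Deaths after new treatment.** A reader might infer that the plan is silent on these. Section 3.1.4 ends scanning at "study termination, or initiation of subsequent anticancer treatments", and section 9.6.2.3 adds "Only tumor scans prior to start of any subsequent anticancer treatment are included", while survival follow-up goes on: "All patients will be followed for survival and subsequent treatments every 12 weeks". But that restriction covers scans only, and death from any cause carries no such limit. Read plainly, later deaths count. Whether that is the best rule is a matter of preference, so it is not part of this point.

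**Table 1 is loosely worded.** It starts PFS at study entry where section 9.6.2.3 uses first dose. The practical gap is small, since a footnote to the schedule of assessments says "First dose of study drug in Cycle 1 should be administered within 3 days of enrollment". The DOR conflict therefore rests mainly on the appendices. Those are short summaries of published criteria, and section 9.6.2.1 could be read as meaning any CR or PR. The more natural reading is the conflicting one, and the ambiguity itself needs removing.

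**mCRPC.** If modified RECIST v1.1 in sections 9.6.2.1 and 9.6.2.3 means the whole of Appendix 3, bone progression is already included. What then remains is mainly the sentence in section 7.3.3.1. The group is also limited, because section 4.2 excludes BRCA1/2-mutated mCRPC.

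**Conclusion.** Both contradictions are in the current text and should be corrected before analysis.

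- **PFS:** the censoring sentence, taken literally, biases Kaplan-Meier PFS upward. Assumed death shares of 5% to 20% inflate the median by about 1.05 to 1.25 under constant hazards, ignoring scan timing. The direction is certain if the sentence is followed. The size is illustrative, because no death share or expected median is given.
- **DOR:** section 9.6.2.1, as naturally read, shortens DOR by the PR-to-CR interval, for PR-to-CR responders only.
- **mCRPC:** a minor inconsistency in the definition of progression, not quantified.

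A reader might infer that the trial's main conclusions are at risk. They are not. PFS and DOR are descriptive secondary endpoints with no test attached, and the two main points leave ORR, the rule of 0 responses in 11 patients and the sample size unchanged.

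**What to change.** - **Section 9.6.2.3:** change the condition of the censoring sentence so that it covers only patients with neither documented radiologic progression nor death. Keep the existing censoring dates (last adequate scan, or first dose if there is no post-baseline scan).
- **Section 9.6.2.1:** start DOR at the first date on which CR or PR criteria are met and later confirmed. If the duration of CR is also wanted, report it separately as the appendices define it.
- **mCRPC:** reconcile the progression sentence in section 7.3.3.1 with sections 3.1.3 and 9.6.2.2 and Appendix 3, so that DOR, DCR and PFS share one definition of a progression event. This concerns endpoint definitions only, not treatment decisions.
- **SAP:** check that it carries the same wording.

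The cost is wording only, since death and scan dates are already collected. Reported PFS may be lower than under the literal sentence, and DOR will be longer for PR-to-CR patients than under section 9.6.2.1 as it stands.
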